Note for prior lapatinib: Subjects must have completed therapy with lapatinib at least 7 days prior to the first dose of study drug.

Note for prior trastuzumab: Subjects who received Q3 weekly, Q2 weekly or Q1 weekly must have completed therapy with trastuzumab at least 3 weeks, 2 weeks or 1 week, respectively, prior to the first dose of study drug.

9. Adequate hematologic and hepatic function as defined in Table 1.

Table 1 Definitions for Adequate Hematologic and Hepatic Function

System	Laboratory Values
Hematologic	
Absolute neutrophil count (ANC)	$\geq 1.0 \times 10^9/L$
Hemoglobin ^a	$\geq 9 \text{ g/dL} (5.6 \text{ mmol/L})$
Platelets	$\geq 100 \times 10^9/L$
Prothrombin time (PT) or international normalized ratio (INR) ^b	$\leq 1.2 \times \text{ULN}$
Activated partial thromboplastin time (aPTT)	$\leq 1.2 \times \text{ULN}$
Hepatic	
Total bilirubin	$\leq 1.5 \times \text{ULN}$ (except in patients with Gilbert's)
Alanine amino transferase (ALT) and Aspartate aminotransferase (AST) ^c	$\leq 2.5 \times \text{ULN}$
Renal	
Serum creatinine	$\leq 1.5 \text{ mg/dL} (133 \text{ } \mu\text{mol/L})$
Or, if $>1.5 \text{ mg/dL}$: Calculated creatinine clearance	$\geq 30 \text{ mL/min}$
Quantitative urine protein by dipstick	≤ 100
Urine Protein to Creatinine Ratio (UPC) ^d	≤ 1

- a. Subjects may not have had a transfusion within 7 days of screening assessment.
- b. Subjects receiving anticoagulant therapy are eligible if their INR is stable and within the recommended range for the desired level of anticoagulation.
- c. Concomitant elevations in AST/ALT above $1.0 \times \text{ULN}$ (upper limit of normal) are not permitted. Bilirubin ≤ 1.5 except if Gilbert's (elevation due to direct bilirubin)
- d. A UPC is required only if the urine protein is > 100 . If UPC > 1 , then a 24-hour urine protein must be assessed. Subjects must have a 24-hour urine protein value $< 1 \text{ g}$ to be eligible.

10. Subjects must have discontinued hormone replacement therapy (HRT) (e.g., conjugated estrogens tablets, USP or premarin), at least 28 days prior to receiving the first dose of randomized therapy.
11. Radiotherapy prior to initiation of therapy is allowed to a limited area (e.g., palliative treatment for painful bone metastases), if it is not the sole site of disease. Subjects must have completed treatment at least one week prior to starting study drugs, and must have recovered from all treatment-related toxicities.

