(C). ALT $>8.0 \times$ ULN without bilirubin elevation (defined as total bilirubin $<2.0 \times$ ULN or direct bilirubin $\leq 35\%$) and without hypersensitivity symptoms (e.g., fever, rash), not attributed to malignancy.	
1st occurrence
 
1. Discontinue pazopanib until toxicity resolves to \leq Grade 1 or baseline. Report the event to Novartis as an SAE within 24 hours of learning of its occurrence (section 16.2, SAE reporting), and complete the eCRF liver event forms. Make every reasonable attempt to have subjects return to the clinic within 24 to 72 hours for repeat liver chemistries and liver event follow up assessments. Pazopanib may only be restarted following recovery if toxicity is clearly unrelated to study drug (e.g. alcohol or significant acetaminophen ingestion)2. Work up for other etiologies as clinically indicated .3. Monitor subject closely for clinical signs and symptoms; perform full panel LFTs weekly or more frequently if clinically indicated until alanine aminotransferase (ALT)/aspartate aminotransferase (AST) reduced to Grade 1.

Event	Dose Modification Algorithms
(D). ALT >3.0 x ULN with concomitant elevation in bilirubin (defined as total bilirubin <2.0 x ULN; with direct bilirubin >35%) not related to disease progression, or with hypersensitivity symptoms (e.g., fever, rash).	
 1. Discontinue pazopanib immediately, report the event to Novartis as an SAE within 24 hours of learning of its occurrence (section 16.2, SAE reporting), and complete the eCRF liver event forms. Make every reasonable attempt to have subjects return to the clinic within 24 hours for repeat liver chemistries and liver event follow up assessments. 2. Consult a gastroenterologist / hepatologist and perform the following assessments to identify potential co-factors: 
 • Eosinophil count • Viral serology for hepatitis A, B, C and E, cytomegalovirus, Epstein-Barr virus IgM antibody, or heterophile antibody, or monospot testing) • Anti-nuclear antibody, anti-smooth muscle antibody, anti-mitochondrial antibody • Serum creatinine phosphokinase for possible muscle injury caused LFT elevation • Liver imaging (ultrasound or CT scan) 3. Monitor subject closely for clinical signs and symptoms; perform full panel LFTs weekly or more frequently if clinically indicated until LFTs reduced to Grade 1.

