For isolated total bilirubin elevation without concurrent ALT increases (defined as ALT < 3 X ULN)	
 1. Isolated hyperbilirubinemia (ie in the absence of elevated ALT or other signs/symptoms of liver injury) does not require dose modification. Pazopanib inhibits UGT1A1 and OATP1B1, which can cause elevation of indirect (unconjugated) bilirubin in the absence of liver injury. 2. If bilirubin is > 2 x ULN in the absence of ALT elevation, fractionation of bilirubin elevation should be performed. If the bilirubin is predominantly indirect (unconjugated), continue pazopanib at the same dose. If bilirubin is >35% direct (conjugated), further evaluation for underlying cause of cholestasis should be performed.

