All SAEs	24 hours	SAE data collection tool	24 hours	Updated SAE data collection tool
Pregnancy	2 weeks	Pregnancy Notification Form	2 weeks	Pregnancy Follow up Form
Liver chemistry abnormalities:				

ALT: >3.0 x ULN with concomitant elevation in bilirubin ^a (defined as total bilirubin \geq 2.0 x ULN with direct bilirubin >35%) or with hypersensitivity symptoms (e.g., fever, rash).	24 hours	SAE data collection tool. ^b Liver Event Case Report Form (CRF) and liver imaging and/or biopsy CRFs if applicable	24 hours	Updated SAE data collection tool. ^b Updated Liver Event CRF
ALT >8.0 x ULN without bilirubin elevation (defined as total bilirubin $<$ 2.0 x ULN or direct bilirubin \leq 35%) and without hypersensitivity symptoms (e.g., fever, rash)	24 hours	SAE data collection tool. Liver Event CRF ^b	24 hours	Updated SAE data collection tool. Updated Liver Event CRF ^b

- a. Bilirubin fractionation should be performed if testing is available. If testing is unavailable and a subject meets the criterion of total bilirubin \geq 2.0 x ULN, then the event should be promptly reported as defined.
- b. Liver event documents should be completed as soon as possible.

All Events must be reported to Novartis within 24 hours of learning of its occurrence. Information about all SAEs is collected and recorded on a Serious Adverse Event Report Form; all applicable sections of the form must be completed in order to provide a clinically thorough report. The investigator must assess and record the relationship of each SAE to each specific study treatment (if there is more than one study treatment), complete the SAE Report Form in English, and send the completed, signed form by **fax within 24 hours to the oncology Novartis DS&E department with the provided FAX cover sheets.**

- Novartis DS&E Oncology Department - [REDACTED]

SAEs brought to the attention of the Study Chair at any time after cessation of pazopanib and considered by the Study Chair to be related or possibly related to pazopanib must be reported to Novartis Pharmaceuticals if and when they occur. Additionally, in order to fulfill international reporting obligations, SAEs that are related to study participation (e.g., procedures, invasive tests, change from existing therapy) or are related to a concurrent medication will be collected and recorded from the time the subject consents to participate in the study until he/she is discharged.

Review of Adverse Event Rates

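### Table 1 footnote c ties the Gilbert's bilirubin exemption to direct bilirubin, probably a slip for indirect, and drops the ULN multiple from the limit

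*Combined protocol and SAP*

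**What the plan says.** Table 1 in Section 3.2 sets the hepatic entry limits. The total bilirubin row gives 1.5 x ULN, "except in patients with Gilbert's", and names no fraction.

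Footnote c is marked on the ALT/AST row and holds two sentences. The first disallows concomitant AST/ALT elevations above 1.0 x ULN. The second restates the bilirubin limit as 1.5, without the ULN multiple, "except if Gilbert's (elevation due to direct bilirubin".

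Table 3 in Section 7.0 has a row for isolated bilirubin elevation on treatment. It refers to inhibition of UGT1A1 and OATP1B1 by pazopanib, "which can cause elevation of indirect (unconjugated) bilirubin in the absence of liver injury". Its instructions are:

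- "Isolated hyperbilirubinemia (ie in the absence of elevated ALT or other signs/symptoms of liver injury) does not require dose modification".
- Above 2 x ULN without ALT elevation, the bilirubin is to be fractionated.
- Where the rise is mainly in the indirect fraction, the patient stays on the current dose.
- Where the direct share is larger, the row asks for a work-up: "If bilirubin is >35% direct (conjugated), further evaluation for underlying cause of cholestasis should be performed".

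**The concern.** The entry rule and the on-treatment rule treat the two bilirubin fractions in opposite ways. Footnote c attaches a permissive clause to direct bilirubin, the fraction that Table 3 sends for a cholestasis work-up. It does not mention indirect bilirubin, the fraction that Table 3 lets continue at full dose.

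If the parenthesis is read as a second condition on the exemption, two errors are possible. A patient with Gilbert's and an indirect elevation could be refused. A patient labelled as Gilbert's with a direct elevation could be admitted without the question that Table 3 would raise later. The missing ULN multiple adds a second discrepancy, because 1.5 alone could be taken as an absolute value.

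This deserves correction because it is operative eligibility text for a drug whose label, according to Section 1.2, carries a boxed warning for hepatic dysfunction.

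**Working it through.** No power, alpha or sample-size figure is involved. The check is to find every table row or footnote that names a bilirubin fraction and compare the direction.

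1. Table 1 footnote c (entry): direct, in a permissive clause.
2. Table 3 row B (ALT above 3 and up to 8 x ULN): direct at or below 35% is one way to count as having no bilirubin elevation.
3. Table 3 row C (ALT above 8 x ULN): same definition as row B.
4. Table 3 row D (ALT above 3 x ULN): concomitant bilirubin elevation is defined "with direct bilirubin >35%) not related to disease progression", and the action is immediate discontinuation with SAE reporting.
5. Table 3, isolated elevation (ALT below 3 x ULN): mainly indirect continues at the same dose; more than 35% direct is evaluated for cholestasis.
6. Section 16.2.2, first liver row (ALT above 3 x ULN): reportable "with direct bilirubin >35%) or with hypersensitivity symptoms".
7. Section 16.2.2, second liver row (ALT above 8 x ULN): direct at or below 35% again counts as no bilirubin elevation.

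Counts:

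- Places other than footnote c: 4 in Table 3 + 2 in Section 16.2.2 = 6.
- Of these 6, direct is the fraction of concern in 6, and in a permissive clause in 0.
- Of these 6, rows about ALT above 3 x ULN on treatment: items 2, 3, 4, 6 and 7 = 5. Rows about bilirubin raised on its own: item 5 = 1.
- Rows among the 6 that mention Gilbert's: 0.

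Item 5 carries the argument. Like a Gilbert's exemption, it deals with raised bilirubin in a patient without a marked ALT rise, and it says in terms that an indirect rise can occur without liver injury. The other five rows repeat one 35% cut for managing or reporting suspected drug injury, so they are not five further independent confirmations. With indirect in place of direct, footnote c agrees in direction with all 6 rows; as written it agrees with none.

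Exposure if the literal wording let in a patient with a direct elevation:

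- The screening panel in Section 8.1 lists total bilirubin but no fraction, so the scheduled tests would not settle the point at entry. It does include alkaline phosphatase.
- Section 8.0, footnote 7 schedules liver tests at weeks 3, 5, 7 and 9, then every 4 weeks.
- Table 3 calls for fractionation above 2 x ULN. The entry limit is 1.5 x ULN. The band in which an exempted patient would not trigger fractionation under that row is therefore above 1.5 and up to 2 x ULN.

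**The case against.** The strongest reply is that the operative rule does not change. The total bilirubin row exempts patients with Gilbert's outright, so eligibility turns on the diagnosis. If the parenthesis only explains the exemption, and explains it wrongly, row and footnote agree and every enrolment decision is the same. This stands as a limit on the consequence: no decision is shown to differ. It does not make the wording right, because the text does not say whether the parenthesis is an explanation or a condition.

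A second reply is that the comparison rows govern management and reporting on treatment, not entry, and none names Gilbert's. This also stands, and it is why the finding rests on the isolated-elevation row with the rest as support. A reader might infer from a tally of six rows against one that the protocol itself proves the word wrong. It does not go that far: the documents never say which fraction Gilbert's raises, so slip is a probable reading and not a demonstrated one.

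A reader might also infer that the rule lets cholestatic patients in undetected, or that the two sites would decide differently. The documents do not support either. The exemption still needs a Gilbert's label, liver tests are frequent, fractionation is called for above 2 x ULN, and under Section 4.3 the Study Chair signs off each registration. Nor does Table 3 stop the drug for an isolated direct fraction above 35%; it asks for evaluation.

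One apparent safeguard should not be overstated. The first sentence of footnote c is not a flat bar on AST/ALT above 1.0 x ULN. It speaks of concomitant elevations, and the row it belongs to allows up to 2.5 x ULN.

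**Conclusion.** The point holds as a minor eligibility and safety wording correction. Footnote c is out of line with Table 3's isolated-bilirubin row on which fraction is benign, and out of line with its own table row on the unit of the limit. The unit discrepancy is plain on the page. The direct-for-indirect slip is probable and rests on the internal mismatch alone.

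The affected group is patients with Gilbert's and total bilirubin above 1.5 x ULN, likely few of the 30 planned; the documents give no count and none is assumed here. The two-stage design, the clinical benefit endpoint and the analysis are unaffected.

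**What to change.** Amend only the second sentence of footnote c, to read: *Bilirubin ≤ 1.5 x ULN except if Gilbert's (elevation due to indirect bilirubin)*. Refer to that sentence from the total bilirubin row as well, since the marker now sits only on the ALT/AST row. Keep the first sentence, on concomitant AST/ALT elevations, unchanged and on the ALT/AST row; replacing the whole footnote would delete a separate hepatic entry restriction.

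The cost is a one-sentence amendment plus one footnote marker. No added assay, new threshold or visit is required, and sample size and analysis stay as they are.

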3.3 Exclusion Criteria

Subjects meeting any of the following criteria must not be enrolled in the study:

1. Prior use of pazopanib or other agents targeting angiogenesis pathway (such as bevacizumab, sunitinib, or sorafenib) in the metastatic setting
2. Premenopausal levels of estradiol, or ongoing menses (see definitions of menopause above).
3. Known central nervous system (CNS) metastases or leptomeningeal carcinomatosis. Screening with CNS imaging studies (computed tomography [CT] or magnetic resonance imaging [MRI]) is required only if the subject has clinical findings suggestive of CNS metastasis.
4. History of another active malignancy.
Note: Subjects who have had another malignancy and have been disease-free for 5 years, or subjects with a history of completely resected non-melanomatous skin carcinoma or successfully treated *in situ* carcinoma are eligible.
5. Clinically significant gastrointestinal abnormalities which might interfere with oral dosing, including, but not limited to:
 - a. Malabsorption syndrome
 - b. Major resection of the stomach or small bowel that could affect the absorption of study drug
 - c. Inflammatory bowel disease
 - d. Ulcerative colitis, or other gastrointestinal conditions with increased risk of perforation
 - e. History of abdominal fistula, gastrointestinal perforation, or intra-abdominal abscess within 28 days prior to beginning study treatment
6. Presence of uncontrolled infection.

7. Prolongation of corrected QT interval (QTc) >480 msecs.
8. History of any one or more of the following cardiovascular conditions within the past 6 months:
 - a. Angioplasty or stenting
 - b. Myocardial infarction
 - c. Unstable angina
 - d. Coronary artery by-pass graft surgery
 - e. Symptomatic peripheral vascular disease
9. Class II, III or IV congestive heart failure, as defined by the New York Heart Association (NYHA).
10. Use of an investigational agent, including an investigational anti-cancer agent, within 14 days prior to the first dose of study drug.
11. Prior use of an investigational drug that targets VEGF or VEGF receptors.
12. Any ongoing toxicity from prior anti-cancer therapy that is $>$ Grade 1 and/or that is progressing in severity.
13. Poorly controlled hypertension (defined as systolic blood pressure (SBP) of ≥ 140 mmHg or diastolic blood pressure (DBP) of ≥ 90 mmHg).

Note: Initiation or adjustment of antihypertensive medication(s) is permitted prior to study entry. Blood pressure must be re-assessed prior to start of study therapy. The mean SBP/DBP values must be $<140/90$ mmHg (OR 150/90mmHg, if this criterion is approved by Safety Review Team) in order for a subject to be eligible for the study.

14. History of cerebrovascular accident (CVA), pulmonary embolism or untreated deep venous thrombosis (DVT) within the past 6 months.
Note: Subjects with recent DVT who have been treated with therapeutic anti-coagulant agents for at least 6 weeks are eligible.
15. Major surgery or trauma within 28 days prior to first dose of study drug and/or presence of any non-healing wound, fracture, or ulcer not related to cancer (procedures such as catheter placement not considered to be major).
16. Evidence of active bleeding or bleeding diathesis.
17. Any serious and/or unstable pre-existing medical, psychiatric, or other condition that could interfere with subject's safety, provision of informed consent, or compliance to study procedures

4.0 Patient Registration

4.1 Stratification

No stratification will be performed in this study

4.2 Randomization and Blinding

No randomization or blinding will be performed in this study.

4.3 Registration and Enrollment

The Coordinating Center for this study will be UCSF. All patients who are consented will be entered into the UCSF Cancer Center OnCore database, which is password protected and meets HIPAA guidelines. All data will be collected and entered into OnCore® by Clinical Research Coordinators (CRCs) from UCSF and Yale.

Patients can be registered only after the pretreatment evaluation is complete and all eligibility criteria have been met. The patient must have signed and dated the currently approved consent form prior to any study-related screening procedures are performed.

The registration procedure at Yale will be as follows: when the Principal Investigator determines that a patient meets eligibility criteria; the study site will fax or e-mail a completed eligibility checklist and supporting source documentation to UCSF CRC. The CRC will check the forms for completeness and contact Yale regarding any discrepancies. The Study Chair will approve each patient registration by signing the eligibility checklist and will assign a patient number. Upon obtaining signed informed consent, the patient information will be entered into OnCore. UCSF will provide a study-specific patient ID number to Yale. All future study documentation related to that patient should include the assigned patient ID number.

5.0 Investigational Treatment Plan

5.1 Dose and Schedule

Pazopanib, 800 mg a day by mouth

Letrozole 2.5 mg, **OR** anastrozole 1 mg a day by mouth;

5.2 Duration of Therapy

Treatment is continued until progression, withdrawal of consent, or unresolved toxicity.

6.0 General Concomitant Medication and Supportive Care Guidelines

Subjects will be asked to provide a complete list of prescription and over-the-counter medications that have been taken within the previous 4 weeks prior to their screening visit. The investigator must be informed as soon as possible about any new medication taken from the time of screening until the end of the clinical phase of the study (final laboratory sample).

Subjects should receive full supportive care during the trial, including transfusion of blood and blood products, treatment with antibiotics, analgesics, erythropoietin, or bisphosphonates, when appropriate.

Anti-emetics (such as prochlorperazine, lorazepam, ondansetron or other 5-HT antagonists) may be administered prophylactically in the event of nausea. Anti-diarrheals, such as loperamide, may be administered as needed in the event of diarrhea (please refer Appendix III for detail management). Although acetaminophen at doses of ≤ 2 g/day is permitted, it should be used with caution in subjects with impaired liver function.

7.0 Toxicity Management & Dose Modifications

At each visit during the Treatment Period, subjects should first be evaluated for the occurrence of AEs and laboratory abnormalities. The potential causes of the adverse events should be thoroughly investigated and confounding factors should be identified and eliminated whenever possible.

Treatment emergent hypertension or proteinuria is relatively common in subjects receiving pazopanib and is handled by dose modification of pazopanib. Some adverse events, although rare, can result in significant clinical consequence such as arterial/venial thrombosis, severe hemorrhage, bowel perforation and severe fatigue/asthenia, therefore should be promptly identified and managed. Some clinical signs and symptoms may be early indicators for severe toxicity that should be thoroughly investigated (e.g., abdominal pain may be an early sign for bowel perforation).

Specific recommendations for management of these possible AEs along with guidelines for dose delay/modification or discontinuation of study treatment are provided in Tables 2 and 3.

If dose reduction of pazopanib is necessary, the dose should be reduced stepwise by 200 mg at each step, and the subject should be monitored for 10 to 14 days at each dose level. If toxicity does not abate during this monitoring time, pazopanib may need to be interrupted and/or the dose further decreased with continued monitoring for an additional 10-14 days at each dose level, and so on.

If the toxicity has abated with reduction of the dose and dose re-escalation is considered safe by the investigator, the dose can then be increased step-wise back to the pre-event dose (in 200 mg increments, after monitoring for 10-14 days at each dose level to ensure that toxicity did not recur or worsen).

If a subject's treatment has been interrupted for more than 21 days, the Investigator must contact the PI to review the subject's condition in order to resume the treatment.

Dose Interruptions/Modifications for Specific, Non-liver Related, Toxicities

Recommendations for investigational product dose interruptions/modifications in case of specific treatment-emergent AEs are provided in Table 2.

Table 2 Dose Modification Algorithms for Potential Treatment-Related Adverse Events

AE Terms & Descriptions	Dose Modification Algorithms
Hypertension^a	
(A). Asymptomatic and persistent SBP of ≥ 150 and < 170 mmHg, or DBP ≥ 90 and < 110 mmHg.	Step 1. Continue investigational product pazopanib at the current dose. Step 2. Adjust current or initiate new antihypertensive medication(s). Step 3. Titrate antihypertensive medication(s) during next 2 weeks as indicated to achieve well-controlled ^b blood pressure (BP). If BP is not well-controlled within 2 weeks, consider referral to a specialist and go to scenario (B).
(B). Asymptomatic SBP ≥ 170 mmHg, or DBP ≥ 110 mmHg, or failure to achieve well-controlled BP within 2 weeks in scenario (A).	Step 1. Interrupt pazopanib.. Step 2. Adjust current or initiate new antihypertensive medication(s). Step 3. Titrate antihypertensive medication(s) during next 2 weeks as indicated to achieve well-controlled BP. Step 4. Once BP is well-controlled, restart pazopanib dose-reduced by 200 mg.
(C). Symptomatic hypertension or recurring SBP ≥ 170 mmHg, or DBP ≥ 110 mmHg, despite modification of antihypertensive medication(s)	Step 1. Interrupt pazopanib Step 2. Adjust current or initiate new antihypertensive medication(s). Step 3. Titrate antihypertensive medication(s) during next 2 weeks as indicated to achieve well-controlled BP. Referral to a specialist for further evaluation and follow-up is also recommended. Step 4. Once BP is well-controlled, restart pazopanib dose-reduced by 200 mg.
(D). Refractory hypertension unresponsive to above interventions.	Discontinue pazopanib and continue follow-up per protocol.
Proteinuria	
UPC ≥ 3 grams or 24-hr urine protein ≥ 3 grams	Step 1. Interrupt pazopanib. Step 2. Test weekly the 24-hour urine protein until the level is < 3 grams. Then, restart pazopanib, dose reduced by 200 mg. Step 3. If 24-hour urine protein ≥ 3 grams recurs, repeat Steps 1 and 2. Step 4. If 24-hour urine protein ≥ 3 grams recurs and the pazopanib dose can no longer be reduced, discontinue pazopanib and continue follow up per protocol.

Hemorrhage /Bleeding

Grade 1

For hemoptysis, interrupt pazopanib and contact the study PI to discuss whether further treatment with pazopanib is appropriate.

Continue pazopanib with current dose; monitor as clinically indicated.

Grade 2

Step 1. If pulmonary or GI bleed (other than hemorrhoidal bleeding), discontinue pazopanib and continue follow-up per protocol. Otherwise, interrupt pazopanib until the AE resolved to \leq Grade 1.

Step 2. Restart pazopanib; consider reducing dose and monitor as clinically indicated.

Grade 3 or 4, or Recurrent \geq Grade 2 event after dose interruption/reduction.

Discontinue pazopanib and continue with follow-up per protocol.

Venous Thrombosis (DVT, PE)

Grade 1 and 2

Continue pazopanib with same dose; initiate and monitor anticoagulation as clinically indicated.

Grade 3 or >

Discontinue pazopanib and continue follow-up per protocol.

Grade 4 and/or PE

Discontinue pazopanib and continue follow-up per protocol.

Arterial Thrombosis/Ischemia

Any Grade

Discontinue pazopanib and continue follow-up per protocol.

Thrombocytopenia: Investigate and document underlying cause

Grade 1 or 2

Continue pazopanib with current dose; monitor as clinically indicated.

Grade 3 or 4

Step 1. Interrupt pazopanib until toxicity resolves to \leq Grade 2.
Step 2. Restart pazopanib dose-reduced by 200 mg and monitor as clinically indicated.

If no recovery to \leq Grade 2 or recurrent Grade 3 or 4 thrombocytopenia, discontinue pazopanib and follow-up per protocol

Anemia: No specific dose reduction rules are indicated for anemia unless due to hemorrhage or bleeding as noted above.

Palmar-plantar Erythrodysesthesia Syndrome

Grade 1	1. Continue IP at present dose
Minimal skin changes or dermatitis without pain (erythema, oedema, hyperkeratosis)	
Grade 2	1. Hold IP 2. Treat as clinically appropriate 3. Upon resolution to Level 1 or better restart IP with a dose reduction to 400 mg 4. If recurrent consider a further dose reduction to 200mg or discontinuation
Skin changes with pain; limiting instrumental activities of daily living (ADLs) (peeling, blisters, oedema, bleed, hyperkeratosis)	
Grade 3	1. Discontinue IP
Severe skin changes with pain and limiting self care	

Other Clinically Significant Adverse Events ^c

Grade 1	Continue pazopanib; monitor as clinically indicated.
Grade 2 or 3, if clinically significant	Step 1. Interrupt pazopanib until toxicity resolves to \leq Grade 1. Step 2. Restart pazopanib dose-reduced by 200 mg and monitor as clinically indicated.
Grade 4	Discontinue pazopanib and continue follow-up per protocol.

Prolongation of QTc Interval: If the QTc is prolonged, the ECG should be manually read to ensure accuracy of the reading. The values below refer to manually-read ECGs.

QTc \geq 480 < 500 msec	Continue pazopanib; monitor as clinically indicated.
QTc \geq 500 msec	Discontinue pazopanib and continue follow-up per protocol.
a.	Patients are encouraged to self-monitor BP twice a week
b.	Well-controlled BP defined as mean SBP \leq 150 mmHg and mean DBP \leq 90 mmHg.
c.	AEs are graded according to NCI Common Terminology Criteria for Adverse Events v4.0 (NCI CTCAE v4) for the management of treatment related diarrhea, please refer to Appendix III. Abbreviations: BP, blood pressure; PAZOPANIB, investigational product.

Dose Interruptions/Modifications for Hepatotoxicity

Recommendations for investigational product dose interruptions/modifications in case of liver-related treatment-emergent AEs are provided in Table 3. As a general rule, since many subjects are taking multiple concurrent medications, it is critical to (a) do a thorough evaluation of the subject's concurrent medications, and (b) identify and discontinue those with known hepatotoxicity and replace with a non-hepatotoxic equivalent for the same indication if necessary.

Table 3 Guidelines for Management of Treatment Emergent Hepatotoxicity

Event	Dose Modification Algorithms
(A). ALT of $\leq 3.0 \times$ upper limit of normal (ULN)	Continue IP at current dose with full panel liver function tests (LFTs) ^a monitored as per protocol.
(B). ALT $>3.0 \times$ ULN to $\leq 8.0 \times$ ULN without bilirubin elevation (defined as total bilirubin $<2.0 \times$ ULN or direct bilirubin $\leq 35\%$) and without hypersensitivity symptoms (e.g., fever, rash)	
1. Continue pazopanib at current dose.2. Work up for other etiologies as clinically indicated.3. Monitor subject closely for clinical signs and symptoms; perform full panel LFTs weekly or more frequently if clinically indicated until alanine aminotransferase (ALT)/aspartate aminotransferase (AST) reduced to Grade 1.
(C). ALT $>8.0 \times$ ULN without bilirubin elevation (defined as total bilirubin $<2.0 \times$ ULN or direct bilirubin $\leq 35\%$) and without hypersensitivity symptoms (e.g., fever, rash), not attributed to malignancy.	
1st occurrence
 
1. Discontinue pazopanib until toxicity resolves to \leq Grade 1 or baseline. Report the event to Novartis as an SAE within 24 hours of learning of its occurrence (section 16.2, SAE reporting), and complete the eCRF liver event forms. Make every reasonable attempt to have subjects return to the clinic within 24 to 72 hours for repeat liver chemistries and liver event follow up assessments. Pazopanib may only be restarted following recovery if toxicity is clearly unrelated to study drug (e.g. alcohol or significant acetaminophen ingestion)2. Work up for other etiologies as clinically indicated .3. Monitor subject closely for clinical signs and symptoms; perform full panel LFTs weekly or more frequently if clinically indicated until alanine aminotransferase (ALT)/aspartate aminotransferase (AST) reduced to Grade 1.

Event	Dose Modification Algorithms
(D). ALT >3.0 x ULN with concomitant elevation in bilirubin (defined as total bilirubin <2.0 x ULN; with direct bilirubin >35%) not related to disease progression, or with hypersensitivity symptoms (e.g., fever, rash).	
 1. Discontinue pazopanib immediately, report the event to Novartis as an SAE within 24 hours of learning of its occurrence (section 16.2, SAE reporting), and complete the eCRF liver event forms. Make every reasonable attempt to have subjects return to the clinic within 24 hours for repeat liver chemistries and liver event follow up assessments. 2. Consult a gastroenterologist / hepatologist and perform the following assessments to identify potential co-factors: 
 • Eosinophil count • Viral serology for hepatitis A, B, C and E, cytomegalovirus, Epstein-Barr virus IgM antibody, or heterophile antibody, or monospot testing) • Anti-nuclear antibody, anti-smooth muscle antibody, anti-mitochondrial antibody • Serum creatinine phosphokinase for possible muscle injury caused LFT elevation • Liver imaging (ultrasound or CT scan) 3. Monitor subject closely for clinical signs and symptoms; perform full panel LFTs weekly or more frequently if clinically indicated until LFTs reduced to Grade 1.
For isolated total bilirubin elevation without concurrent ALT increases (defined as ALT < 3 X ULN)	
 1. Isolated hyperbilirubinemia (ie in the absence of elevated ALT or other signs/symptoms of liver injury) does not require dose modification. Pazopanib inhibits UGT1A1 and OATP1B1, which can cause elevation of indirect (unconjugated) bilirubin in the absence of liver injury. 2. If bilirubin is > 2 x ULN in the absence of ALT elevation, fractionation of bilirubin elevation should be performed. If the bilirubin is predominantly indirect (unconjugated), continue pazopanib at the same dose. If bilirubin is >35% direct (conjugated), further evaluation for underlying cause of cholestasis should be performed.

